9.5.1.2. Clinical Laboratory Evaluation

Descriptive statistics will be provided for the clinical laboratory results by scheduled time of evaluation and by treatment group, as well as for the change from baseline. The baseline value is defined as the last non-missing value before the initial administration of study drug. In addition, mean change from baseline will be presented by treatment group for the maximum and minimum post-treatment values and the values at Day 12.

Abnormal clinical laboratory results will be graded according to National Cancer Institute - common terminology criteria for adverse events (NCI-CTCAE) Version 5.0, if applicable, and the grade will be presented in a by-subject data listing. A shift table, presenting by treatment group the two-way frequency tabulation for baseline and the worst post-treatment value according to the CTCAE grade, will be provided for clinical laboratory tests. A listing of abnormal clinical laboratory test results deemed of clinical significance or of Grade 3 or 4 will be generated.

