1.3. Schedule of Events

Table 1.1: Schedule of Events

		Screening		Period 1 ^a		Period 2 ^a				
Overall Study Day		-21 to -2	-1	1	2 to 5	5 to 7	8	9	10 to 11	12/ET/ EOS
Informed Consent ^b		X								
Inclusion/Exclusion Criteria	Demographic Information	X								
	Medical History	X	X							
	Drugs of Abuse ^c	X	X							
	Pregnancy Test ^d	X	X							X
	FSH ^e	X								
	HIV Ab Test	X								
	HBsAg, HCV Ab	X								
	Prior medications	X	X							
PGx	Collect PGx Sample			X						
Vital/ Physical	Physical Examination	X	X			X				X
	Vital Signs ^f	X	X	X		X				X
	Height	X								
	Weight/BMI ^g	X	X							X
Safety	Clinical Labs ^h	X	X			X		X		X
	Triple ECG ⁱ	X	X	X		X				X
Study Drug	Dabigatran etexilate ^j			X		X				
	Quizartinib ^k					X				
PK Blood Sample				X ^l	X ^l	X ^m	X ^m			
Adverse Events		Continuous								
Concomitant Medications		Continuous								
Clinic	Clinic Admission		X							
	Clinic Discharge									X

Ab = antibody; aPTT = activated partial thromboplastin time; CrCL = creatinine clearance; CRU = clinical research unit; ECG = electrocardiogram; EOS = end of study; ET = early termination; FSH = follicle stimulating hormone; HBsAg = hepatitis B virus surface antigen; HCV = hepatitis C virus; HIV = human

immunodeficiency virus; INR = international normalized ratio; PGx = pharmacogenomics; PK = pharmacokinetics; QTcF = QT interval corrected with Fridericia's formula

- a. Period 1 ends at the collection of clinical laboratory sample (approximately 96 hours post Day 1 dosing) on Day 5. Period 2 starts on Day 5 with the Predose safety sample. The post dose clinical laboratory sample on Day 5, Period 1 (approximately 96 hours post Day 1 dosing) can be also be used as a pre-dose clinical laboratory sample for Period 2.
- b. Signed written informed consent prior to any study procedures.
- c. Urine test for drugs of abuse (illegal and/or prescription), including tobacco and alcohol will be tested during Screening and Day-1.
- d. Serum pregnancy test at Screening; urine pregnancy test at CRU admission (Day -1), and on Day 12 (ET/EOS).
- e. Naturally postmenopausal female subjects only.

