- f. Vital signs should be taken at Screening, at CRU admission (Day -1), prior to administration of dabigatran etexilate (Day 1) and 2 hours after dabigatran etexilate dosing, on Day 12 (ET/EOS), and as clinically indicated. Vital signs should be taken predose, postdose 2 hours and 6 hours after dabigatran etexilate administration on Day 1 and on Day 5. Vital signs should be taken at 1 hour prior to quizartinib administration and at 2, 4, and 8 hours post quizartinib administration. Blood pressure and pulse rate will be measured after the subject has rested in a supine position for at least 5 minutes or more and prior to laboratory draws and taken after at least a 5-10 minutes supine rest at all ECG time points.
- g. BMI at screening only.
- h. Clinical labs (hematology, clinical chemistry, aPTT/PT/INR, CrCL and urinalysis) should be taken at Screening, Day -1, approximately 96 hours post dosing on Day 5 (Period 1), on Day 9 and on Day 12 (ET/EOS). Subjects will have to fast (except water) for at least 10 hours before having blood drawn for these laboratory tests.
- i. 12-lead ECG should be recorded in triplicate with the clinical site's equipment (3 separate ECGs at least 2 minutes apart; the average of the 3 QTcF determinations used to determine safety parameters). ECGs should be obtained once, in triplicate, at Screening, on Day -1, and on Day 12 (ET/EOS). The ECG will be measured after the subject has rested in a supine position for 5 minutes or more. On Day 1 of Period 1, triplicate ECGs will be recorded within 1 hour prior to dabigatran etexilate administration and at 2 and 6 hours after dabigatran etexilate administration. On Day 5 of Period 2, triplicate ECGs should be recorded within 1 hour prior to quizartinib administration and 2, 4, and 8 hours after quizartinib administration.
- j. Dabigatran etexilate will be administered on Day 1 and Day 5
- k. Quizartinib should be administered 2 hours prior to dabigatran etexilate.
- l. Blood for PK analysis should be taken in Period 1: predose and 0.5, 1, 1.5, 2, 3, 4, 6, 8, 12, 24, 36, 48, 60 and 72 hours post-dabigatran dose.
- m. Blood for PK analysis should be taken in Period 2 (relative to quizartinib): predose and 1, 2.5, 3, 3.5, 4, 5, 6, 8, 10, 14, 26, 38, 50, 62, and 74 hours post-quizartinib dose.

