5.1. Inclusion Criteria

Subjects eligible for inclusion in this study have to meet all inclusion criteria for this study.

1. Voluntarily consents to participate in this study and provides written informed consent before the start of any study-specific procedures.
2. Male and female subjects 18 to 55 years of age, (inclusive), with a body mass index (BMI) of 18 kg/m² to 32 kg/m², inclusive, at Screening.
3. In females, documented surgical sterilization, postmenopausal status for at least 1 year (follicle stimulating hormone [FSH] >40 mIU/mL serum at Screening), or agreement to have sterile male partner, or agreement to use 1 of the protocol-approved means of contraception from Screening until 6 months after the dose of quizartinib. See Section 5.3 Contraception Requirements.
4. In males, documented surgical sterilization, or sexual abstinence, or agreement to use 1 of the protocol-approved means of contraception from Screening until 6 months after the dose of quizartinib. See Section 5.3 Contraception Requirements.
5. In females, must not retrieve eggs/ova via assisted reproductive technology (ART) either for their own use or donation while on study or for 6 months after the last dose of quizartinib, whichever is later.
6. In males, agreement to avoid sperm donation for 6 months after the dose of quizartinib.
7. Determined to be healthy by the investigator based on medical history, medical examination, vital signs, and 12-lead ECG during Screening and through Day -1.
8. Clinical laboratory findings are within normal range or if outside the normal range, deemed not clinically significant in the opinion of the investigator and the Sponsor medical monitor during Screening and on Day -1 Serum creatinine $\leq 1.5 \times$ ULN and estimated creatinine clearance (CrCl) ≥ 80 mL/min according to the Cockcroft-Gault equation, at Screening and on Day -1.
9. Willingness to consume high-potassium foods, such as bananas, cantaloupe, oranges (excluding blood orange), orange juice (excluding blood orange juice), and yogurt, for at least 24 hours before quizartinib administration on Day 5 (except during the fasting period).
10. Serum potassium, magnesium, and calcium (corrected for albumin level) within normal limits. Subjects with values below normal at Screening or on Day -1 may be eligible if levels of these electrolytes were corrected before quizartinib administration.

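### With one pre-Day 1 baseline for both periods, the Period 2 lab shift table can misplace grade changes around the quizartinib dose; a Day 5 pre-quizartinib display should be added

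*Combined protocol and SAP*

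**What the plan says.** Section 9.5.1.2 (Clinical Laboratory Evaluation) sets one baseline: "The baseline value is defined as the last non-missing value before the initial administration of study drug". The same sentence appears in Section 9.5.1.3 for ECGs and Section 9.5.1.4 for vital signs. Section 9.4.1 counts both quizartinib and dabigatran as study drug, and dabigatran etexilate is given first, on Day 1. The scheduled lab baseline is therefore Day -1.

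Two lab outputs rest on that baseline by treatment group. One is the change summary: "mean change from baseline will be presented by treatment group for the maximum and minimum post-treatment values and the values at Day 12". The other is the grade table: "A shift table, presenting by treatment group the two-way frequency tabulation for baseline and the worst post-treatment value according to the CTCAE grade". Section 9.5.1.2 also plans change from baseline at each scheduled evaluation.

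Under Table 1.1, footnote h, labs are drawn at Screening, Day -1, Day 5 (about 96 hours after the Day 1 dose), Day 9 and Day 12. Footnote a says "Period 2 starts on Day 5 with the Predose safety sample" and that the Day 5 lab "can be also be used as a pre-dose clinical laboratory sample for Period 2". Footnotes f and i also schedule vital signs and triplicate ECGs before quizartinib on Day 5. None of these Day 5 values is named as a baseline.

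Inclusion criterion 10 reads: "Subjects with values below normal at Screening or on Day -1 may be eligible if levels of these electrolytes were corrected before quizartinib administration". Criterion 9 asks for willingness to eat high-potassium foods for at least a day before the Day 5 quizartinib dose.

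**The concern.** The safety objective in Section 3.2 concerns quizartinib given with dabigatran etexilate, which is Period 2. A reader of the Period 2 column in a by-treatment table will take a shift as something that happened after quizartinib. With the baseline fixed before Day 1, that reading can fail in both directions when a subject's grade changes between Day -1 and Day 5. A shift that was already present before quizartinib can be shown under Period 2, and a rise after quizartinib can be shown as no shift.

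The second case is possible by the protocol's own design. A subject may enter with low potassium, magnesium or calcium and have it corrected before quizartinib. If the value is low again on Day 9 or Day 12, the table compares it with the low entry value. These are the electrolytes that Section 8.6.2.7.2 says to check when QTcF is prolonged, and QT prolongation is an event of special interest for quizartinib (Section 2.3).

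**Working it through.** The plan gives no figure to reproduce, because the point concerns a definition. The inputs are the baseline rule and outputs (Sections 9.5.1.2 to 9.5.1.4), the sampling days (Table 1.1, footnotes a, f, h and i) and the maximum of 20 subjects (Section 4.1.1).

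**1. Shift table.** Take grades 0 and 1 only, at Day -1, Day 5 and the worst of Days 9 and 12. There are 2 × 2 × 2 = 8 patterns.

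| Day -1 | Day 5 | Worst Period 2 | Planned cell | Cell from Day 5 baseline |
|---|---|---|---|---|
| 0 | 0 | 0 | 0→0 | 0→0 |
| 0 | 0 | 1 | 0→1 | 0→1 |
| 0 | 1 | 0 | 0→0 | 1→0 |
| 0 | 1 | 1 | 0→1 | 1→1 |
| 1 | 0 | 0 | 1→0 | 0→0 |
| 1 | 0 | 1 | 1→1 | 0→1 |
| 1 | 1 | 0 | 1→0 | 1→0 |
| 1 | 1 | 1 | 1→1 | 1→1 |

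The cell differs in 4 of the 8 patterns, exactly those in which the Day 5 grade differs from Day -1. Pattern 0,1,1 is an upward shift only with the planned baseline. Pattern 1,0,1 is an upward shift only with the Day 5 baseline. Each such subject is 1/20 = 5 percentage points. The documents give no basis for predicting how many there will be.

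**2. Numeric changes.** For every subject,

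Period 2 value − Day -1 = (Day 5 − Day -1) + (Period 2 value − Day 5).

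The first bracket is the Period 1 change, and it enters the maximum, minimum and Day 12 changes in full.

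**3. What can be recovered.** Means are additive, so with complete data

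mean change from Day 5 = mean change from Day -1 − mean Day 5 change from Day -1.

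Both terms on the right are planned outputs. An illustration with 20 simulated subjects (assumed values, mean Period 1 change −0.51 SD, no true mean change in Period 2) gives:

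- maximum: −0.41 + 0.51 = +0.10
- minimum: −0.70 + 0.51 = −0.19
- Day 12: −0.55 + 0.51 = −0.04

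These equal the means calculated directly from Day 5. The mean tables therefore lose nothing when data are complete.

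The spread is different. The variance of the change from Day 5 depends on the covariance of the Period 1 change with the change from Day -1, and no planned table gives that. The shift table cannot be recovered either, because it does not show the Day 5 grade for each subject. For both, a reader would have to use the by-subject listings.

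**4. Size of the effect on spread.** Suppose that between the baseline and Day 5 each subject has a lasting drift with SD t, and that measurements have independent error with SD s. The variance of the Period 2 change is then 2s² + t² with the planned baseline and 2s² with a Day 5 baseline. The SD is multiplied by √(1 + t²/(2s²)), which is 1.06, 1.22 and 1.73 for t/s = 0.5, 1 and 2. That range is assumed; the documents give neither t nor s.

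**5. ECG and vital signs.** The same identity holds with the Day 1 predose value as baseline. Mean drift is visible at the Day 5 predose time point, so again only individual changes and their spread are affected.

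**6. Timing of the Day 5 lab.** Quizartinib is given 2 hours before dabigatran etexilate. If the two dabigatran etexilate doses are exactly 96 hours apart, quizartinib falls at 96 − 2 = 94 hours, and a lab drawn at exactly 96 hours would follow it. Both times are stated as approximate and footnote a treats the sample as pre-dose, so this is an ambiguity for the SAP to close rather than an error.

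**The case against.** The strongest case on the other side is that a drug-free baseline is coherent. The objective concerns quizartinib in the presence of dabigatran etexilate, and change from an untreated value describes the combination. That stands: the planned display is legitimate and should stay.

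A Day 5 baseline also has its own bias. Day 5 electrolytes may have been raised by correction or by the high-potassium diet, so a fall by Day 9 or Day 12 may be a return to the earlier level. Pattern 1,0,1 could be exactly that. The Day 5 lab would be both the Period 1 outcome and the Period 2 baseline: with independent errors of equal variance and no drug effect, the two periods' changes correlate at −0.5, against +0.5 with the single baseline. This also stands, and is why the Day 5 display should be added and not substituted.

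A low electrolyte might be corrected and retested before Day 1, in which case the retest becomes the baseline. The 1,0 start is therefore possible, not assured.

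Section 9.5 calls itself a summary, with the SAP to be finalized before database lock. That lowers the weight of the point, but the summary states a baseline rule and no other rule is given.

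Four stronger readings are tempting and are not supported.

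- A reader might infer that the maximum, minimum and Day 12 tables cannot be corrected. Only means are planned there, and they can be, as shown above.
- A reader might infer that the whole Period 1 change enters the shift table. Pattern 0,1,0 is tabulated 0→0, so it does not.
- A reader might infer that the baseline defines the secondary safety endpoint. Clinical significance is the investigator's judgment (Sections 8.6.2.1, 8.6.3 and 8.6.6).
- A reader might extend the point to adverse events. That would be inference only: footnote a places the period boundary on Day 5, Section 8.6.2.3 requires causality to be assessed by drug, and Section 10.4.1.1 counts an exacerbation of a pre-existing condition as an event.

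**Conclusion.** The concern holds as a minor point about attribution. The planned Period 2 lab shift table can show a shift that arose before quizartinib or hide a rise that came after it, and the planned summaries cannot put this right. Individual Period 2 changes in labs, ECGs and vital signs, and their spread, carry the Period 1 change. The mean changes carry it too but are recoverable with complete data.

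The size is 5 percentage points for each affected subject if all 20 are enrolled and contribute data, with the number affected unknown. The conclusion assumes that the SAP follows the baseline rule in Section 9.5 and that the Day 5 lab is drawn before quizartinib. The primary PK endpoint, the absolute QTc categories and the listing of clinically significant or Grade 3 or 4 lab results are unaffected.

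**What to change.** In the SAP, keep the drug-free baseline as planned. For Period 2, add a CTCAE lab shift table and change-from-baseline summaries for labs, ECGs and vital signs, all measured from the last value before quizartinib on Day 5. State that the Day 5 lab used as baseline must precede quizartinib, and define it by that order rather than by the 96-hour mark. State also that this sample serves as both the Period 1 outcome and the Period 2 baseline. Add a note that Day 5 electrolytes may reflect correction or diet, so the two displays must be read together.

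The cost is SAP wording and a few extra tables. No new procedure is needed, because the Day 5 pre-quizartinib labs, ECGs and vital signs are already scheduled. The addition does not separate time from treatment in a fixed sequence.

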9.5.1. Safety Analysis

9.5.1.1. Adverse Events

Treatment-emergent adverse events are defined as new AEs that occur after the first dose of study drug or as AEs that were present prior to first dose of study drug but which worsened in severity after the start of study drug. AEs collected 30 days after the last dose of study drug will not be considered TEAEs unless they are treatment-related. AEs will be coded using the Medical Dictionary for Regulatory Activities (MedDRA). An AE will be assigned to the study

day in which it started, even if it resolved on a subsequent day. The incidence of TEAEs will be summarized by treatment group. The number and percentage of subjects reporting TEAEs will be calculated overall, by system organ class, by preferred term, and by treatment group.

Treatment-emergent adverse events will be further summarized by common terminology criteria for adverse events (CTCAE) grade and relationship to study drug. Similarly, the number and percentage of subjects reporting treatment-emergent SAEs and related treatment-emergent SAEs will be tabulated, treatment-emergent AESIs, and TEAEs leading to discontinuation of study drug.

A by-subject AE (including treatment-emergent) data listing including but not limited to verbatim term, preferred term, system organ class, CTCAE grade, and relationship to study drug will be provided. Deaths, SAEs, AESIs, and AEs associated with study drug discontinuation will be listed.

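### Max/min lab change, worst-grade lab shift and TEAE incidence are planned by treatment group, but dabigatran alone and the combination are observed over unequal windows

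*Combined protocol and SAP*

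**What the plan says.** All subjects receive dabigatran etexilate alone on Day 1, then quizartinib followed 2 hours later by dabigatran etexilate on Day 5 (Section 4.1). The two columns of a by-treatment safety table would therefore describe the same people, at most 20, in a fixed order.

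Section 9.5.1.2 plans three kinds of laboratory summary by treatment group:

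- descriptive statistics "by scheduled time of evaluation and by treatment group, as well as for the change from baseline";
- a summary in which "mean change from baseline will be presented by treatment group for the maximum and minimum post-treatment values and the values at Day 12";
- a shift table for "baseline and the worst post-treatment value according to the CTCAE grade".

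One baseline serves throughout: "The baseline value is defined as the last non-missing value before the initial administration of study drug". Section 9.5.1.1 states that "The incidence of TEAEs will be summarized by treatment group" and allocates an AE to the study "day in which it started, even if it resolved on a subsequent day".

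After dosing starts, Table 1.1 footnote h schedules clinical labs "approximately 96 hours post dosing on Day 5 (Period 1), on Day 9 and on Day 12 (ET/EOS"). Footnote a ends Period 1 at that Day 5 sample, which "can be also be used as a pre-dose clinical laboratory sample for Period 2". AEs are marked as continuous in Table 1.1, and Section 8.6.2.2 records them to 30 days after the last dose. Section 9.5.1.1 uses the same limit for TEAEs, except for treatment-related events.

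**The concern.** A maximum, a minimum, a worst grade and a cumulative incidence all depend on how often and how long a subject is observed. Here both quantities differ between the columns by design, and Section 9.5.1 states no matched window. For dabigatran alone, the scheduled maximum and minimum are the same Day 5 value. For the combination they are taken over two values and separate through ordinary within-subject variation alone.

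The safety objective in Section 3.2 concerns quizartinib given in the presence of dabigatran etexilate. A reader who sees the two treatments side by side could take a difference in observation for an effect of quizartinib.

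**Working it through.** **Windows from the schedule**

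| | Dabigatran alone | Combination |
|---|---|---|
| Scheduled post-dose lab draws | 1 (Day 5, about 96 h) | 2 (Days 9 and 12) |
| AE days to next dosing or Day 12 | 5 − 1 = 4 | 12 − 5 = 7 |
| Formal end of TEAE counting | quizartinib dose on Day 5 | about 30 days after the last dose |

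The 4 days reproduce the stated separation of about 96 h (4 × 24). If that separation runs from dabigatran dose to dabigatran dose, quizartinib falls at about 94 h. The ratio of windows is 7/4 = 1.75 to Day 12, or 30/4 = 7.5 under the formal TEAE limit.

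**Labs, no drug effect, normal within-subject variation with SD s**

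- Expected maximum of two draws minus one draw: s/√π = 0.564 s. The minimum falls by the same amount.
- In units of total SD with between-draw correlation r this is √((1 − r)/π): 0.56, 0.40 and 0.18 at r = 0, 0.5 and 0.9.
- Expected gap between the combination's maximum and minimum: 2s/√π = 1.13 s. For dabigatran alone the gap is 0 on scheduled values.
- For scale, the standard error of a mean single-draw change with n = 20 is s√(2/20) = 0.316 s, and 0.564/0.316 = 1.8.

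**Worst grade, assumed 5% abnormality rate per draw**

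Probability of at least one abnormal result in two draws (bivariate normal):

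| r | Probability | Expected of 20 (one draw: 1.0) |
|---|---|---|
| 0 | 9.8% | 2.0 |
| 0.5 | 8.8% | 1.8 |
| 0.9 | 6.8% | 1.4 |

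**AEs, assumed constant background rate p per 96 h**

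Incidence over h hours is 1 − (1 − p)^(h/96).

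- p = 5%, 168 h: 1 − 0.95^1.75 = 8.6%. The excess over 96 h is 20 × (0.0859 − 0.0500) = 0.7 subjects.
- p = 3% and 10%: the excess over 96 h is 0.4 and 1.4 subjects.
- p = 5%, 30 days: 1 − 0.95^7.5 = 31.9%. This is an upper illustration, because it assumes full ascertainment although Table 1.1 has no visit after Day 12.

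**AEs, background rate that declines exponentially from Day 1 with half-time H**

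Expected events in 0–96 h are proportional to 1 − 2^(−96/H). In 96–264 h (7 days from Day 5) they are proportional to 2^(−96/H) − 2^(−264/H).

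- H = 159 h: 0.342 against 0.342, so the windows break even.
- H = 96 h: 0.500 against 0.351, so dabigatran alone shows more events.
- With follow-up to 30 days (96 + 720 = 816 h) and H = 96 h: 0.500 against 0.500 − 2^(−8.5) = 0.497. Reversal over the longer window therefore needs a faster decline.

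**The case against.** The strongest reply is that these are descriptive tables. Section 9.1 disclaims hypothesis testing, and the safety objective is not a contrast with dabigatran alone. Section 9.5 calls itself a summary and defers detail to an SAP to be finalized before database lock. The term treatment group is not defined, and the side-by-side layout is an inference. Most of the laboratory remedy is already planned: the by-visit statistics give Day 5 and Day 9 means, each at about 96 h, and by-subject listings give grades and AEs. Matched windows also leave period order confounded with treatment. All of this stands and keeps the weight low. It does not make the max/min, worst-grade and TEAE columns comparable.

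Four stronger readings are tempting, and the documents do not support them.

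- *AE observation in Period 1 lasts only 72 hours.* Sections 1.1 and 4.1.3 do end Period 1 safety collection at 72 hours, but Table 1.1 marks AEs as continuous and Section 8.6.2.2 records them from consent. The wording needs reconciling; it does not shorten the AE window.
- *A Day 5 AE cannot be assigned to a period.* Footnote a gives a boundary within Day 5, at the lab sample and the Period 2 predose sample. What the documents do not show is whether onset time is captured.
- *The combination must show more AEs.* That needs a constant background rate or something near it; the last calculation above shows the opposite result under a declining rate.
- *Day 12 values bias the comparison.* For completers they exist only after the combination, so there is no dabigatran-alone value to set them against. They need only a label.

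**Conclusion.** The point holds as a low-weight improvement to descriptive secondary safety tables. The by-treatment max/min and worst-grade lab summaries are not comparable between columns, whatever the drug effect. With no effect, the expected maximum is 0.56 within-subject SD higher and the minimum equally lower for the combination, and an assumed 5% per-draw abnormality rate becomes 6.8 to 9.8%. These figures assume scheduled draws only, normal variation and no time trend; repeats of abnormal labs under Section 8.6.3 can change the number of draws for a subject.

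For AEs, only the inequality of the windows is established. The rise from 5% to 8.6%, or 0.7 of 20 subjects, is one scenario whose size and direction rest on the assumed constant rate. The 7 days also assume follow-up to Day 12. Section 4.1.2 allows discharge after a Day 7 counted from quizartinib dosing; read as study Day 7, the observed window would be shorter for subjects who leave early.

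The by-visit lab statistics, the by-time-point ECG statistics and the primary PK comparison are not affected.

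**What to change.** In the SAP:

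1. Keep the full-window tables for the combination. Label max/min change, overall worst grade, Day 12 values and later TEAEs as follow-up after the combination, not as a contrast with dabigatran alone.
2. Add a by-treatment lab grade shift at Day 5 versus Day 9. Show the Day 9 shift also against the Day 5 predose value, because the single baseline before Day 1 carries any Period 1 change into Period 2.
3. Add TEAE incidence from the Day 1 dose up to, but not including, the Day 5 quizartinib dose, against a window of the same length starting at the quizartinib dose. A fixed 96 h Period 1 window could overlap Period 2 if quizartinib falls at about 94 h.
4. Split Day 5 AEs at the quizartinib dose, in line with footnote a. Say how events between the Day 5 lab sample and that dose are counted, and give a default rule for events with no onset time.
5. Separately, reconcile the 72-hour wording in Sections 1.1 and 4.1.3 with continuous AE collection and the 96 h Period 1 lab draw in Table 1.1.

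The cost is a few extra tables and no new assessments. Matched windows omit late events: on simple decay from the half-lives in Section 2.1, 2^(−96/73) = 40% of quizartinib and 2^(−96/119) = 57% of AC886 would remain at 96 h. The matched tables must therefore sit beside the full-window tables, not replace them. Period order remains confounded with treatment.
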